Observational studies are unlikely to eliminate selection bias. The controversy can only be resolved by conducting a randomized controlled experiment in which women with a prenatal diagnosis of PAS are randomly assigned to undergo hysterectomy or partial myometrial resection as the intended treatment modality. This type of study would probably require a high number of patients and the participation of several hospitals that apply the same surgical technique. Considering that the international guidelines for the management of PAS make partial myometrial resection a technique reserved for a select group of patients, some centers refrain from implementing this type of technique and that there are not many centers in the world that do so practice.

The studies published to date evaluating partial myometrial resection are retrospective and observational in nature^{7,14,15}. Although the patients who undergo this type of surgery have been compared with a group of women who finally underwent a hysterectomy after partial resection has been attempted^{14,15}, it is not possible to characterize in these publications two comparable groups (myometrial resection partial vs hysterectomy as management chosen and executed from the beginning of the surgery).

Since a "head-to-head" comparison between hysterectomy and partial myometrial resection has never been performed previously, there are insufficient data to define a sample size necessary for conducting a definitive randomized clinical trial. It is therefore necessary to initially carry out a feasibility study to verify that all the procedures outlined in the protocol (to be carried out later) are viable. This feasibility study will also allow the collection of clinical data from both arms of the study that will allow planning a future definitive randomized clinical experiment.

4. Research question:

Is it possible to recruit, randomize, intervene, and measure outcomes of interest in patients with PAS as part of a clinical experiment comparing two PAS surgical techniques (hysterectomy vs. partial myometrial resection) in a period of 24 months or less?

5. Objective:

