6.1.Primary objective: To evaluate the feasibility of the parallel experimental design, the willingness to participate of eligible patients, and the outcome measures for conducting a randomized phase III clinical experiment comparing partial myometrial resection with hysterectomy in patients with PAS, carried out in 3 different centers, including Fundación Valle del Lili, in a period of 24 months.

6.2.Specific objectives:

- 1. To measure the proportion of eligible patients who agree to participate in this comparison.
- 2. To measure the percentage of screening failure.
- 3. To describe the confirmation of the presence or absence of placental accretenotic spectrum in each case.
- 4. To identify the degree of variability between the different methods of measuring intraoperative bleeding in each of the techniques.

6.3.Secondary objectives:

- 1. Clinical and sociodemographic characterization of the patient.
- 2. To identify the characteristics of the patient's current pregnancy.
- 3. To describe the clinical outcomes of interest in patients randomized to hysterectomy or partial myometrial resection.
- 4. To categorize the severity of surgical complications according to the Clavien Dindo classification.

7. Hypothesis

7.1.Primary hypothesis: It is possible to recruit, randomize, operate and follow-up patients recruited for an experiment comparing two surgical techniques in PAS (Hysterectomy Vs Partial myometrial resection) in a period of 24 months or less.

8. Outcomes measures/endpoints:

8.1.Primary endpoints:

- Proportion of eligible patients who agree to participate in the study.
- Screening failure percentage
- Percentage of patients assigned to each arm of the study.
- Percentage of patients with crossover between assigned study arms.
- Number of subjects who complete follow-up at 42 days postpartum.

8.2. Secondary endpoints:

- Maternal death
- Intra-surgical bleeding volume measured in mL.
- Blood component transfusion requirement, median transfusion of red blood cell units (RBCU)
- Compliance with at least one WHO Near Miss criterion (See Appendix 1)
- Ureteral injuries.
- Bladder injuries
- Need for surgical reoperation.
- Admission to the Intensive Care Unit.
- Days of post-operative hospital stay.
- Use of uterine tamponade with hydrostatic balloons.
- Presence of supra fascial hematoma
- Presence of postoperative ileus
- Vital status of the newborn
- Weight of the newborn

9. Methods:

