Objective measurement of the total intraoperative bleeding volume will be performed by 3 means:

A. Quantification of bleeding present in intraoperative suction devices: The surgical team will make a visible mark on the suction devices at the time of initiation of surgery. The volume that the amniotic fluid will occupy in said devices will be taken into account. To this end, before performing the hysterotomy, the surgeon will notify the anesthesia and nursing team to make an additional mark on the suction device. Similarly, when the baby and all the amniotic fluid have been extracted, the surgeon will again notify the anesthesiology and nursing team, to make a new visible mark on the suction device.

A record will be kept of any volume of sterile solutions used to irrigate the operative field (saline, lactate Ringer). This volume will be subtracted from the final volume count, to avoid overestimating the bleed.

B. Weight quantification of blood-soaked compresses: Cleaning of the operative field with a compress will be preferred and not with suction devices. The blood-soaked compresses will be removed from the operative field and stored in a sterile container in case intraoperative cell recovery is required. At the end of the surgery, the weight of the soaked compresses will be performed and from the value obtained, the "dry weight" will be subtracted from the number of quantified compresses. The surgical team will previously know the weight of each compress used in your institution

C. Quantification of vaginal bleeding with a calibrated collection bag: All participating centers will use a blood collection bag that will be placed under the perineum of the patient before starting the surgery. This bag has a system for

measuring the volume collected that will be quantified at the end of the surgery. The Brass V® brand collection bags will be provided by the executing institution and sent to the participating institutions to ensure the standardization of vaginal bleeding measurement.

At the end of the surgery, an objective estimate of bleeding will be made by adding the volume of bleeding from the suction devices, that of the compresses and that of the vaginal bleeding collection bag.

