Estimated bleeding by count and weight of soaked pads: 0000cc. Estimated bleeding by calibrated vaginal collection bag: 00cc Estimated bleeding by suction devices: 0000cc Total intraoperative bleeding: 0000cc

FIGO classification for PAS: Grade...... Topographic classification of PAS: Classification according to [name]: Type.....

Blood component transfusion: YES / NO Administration of lyophilized fibrinogen: YES / NO Uterine tamponade with hydrostatic balloons: YES / NO Bladder injury: YES / NO Ureteral injury: YES / NO Intestinal injury: YES / NO

Intraoperative bleeding:1. Quantified bleeding when weighing the compresses:2. Quantified bleeding on suction devices:Quantified bleeding in pelvic collecting bag:

Use of cell saver:

Transfusion during surgery:

Recording of operative time. Time of onset of anesthesia:

- 2. Time of start of surgery (Skin incision):
- 3. Time of birth:
- 4. Time of completion of surgery (Skin Closure):

Type of Anesthesia used in the surgical procedure:

Vascular Interventions:

Clinical Diagnosis:

- 1. Presence of PAS:
- 2. FIGO Classification:
- 3. Topographic classification:
- 4. [name] Classification:

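### The research question and objective 6.1 ask whether outcomes can be measured, but no primary endpoint or planned summary reports how completely they were measured

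*Combined protocol and SAP*

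**What the plan says.** The research question in section 4 has four parts, the last being outcome measurement: "Is it possible to recruit, randomize, intervene, and measure outcomes of interest in patients with PAS". Objective 6.1 likewise puts under evaluation the design, patients' willingness "and the outcome measures for conducting a randomized phase III clinical experiment". The primary hypothesis in section 7.1 is narrower: "It is possible to recruit, randomize, operate and follow-up patients recruited for an experiment". Measurement is not named there.

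Section 8.1 lists five primary endpoints:
- "Proportion of eligible patients who agree to participate in the study"
- "Screening failure percentage"
- the split between arms
- crossover between arms
- "Number of subjects who complete follow-up at 42 days postpartum"

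The theoretical framework (section 2) proposes intraoperative bleeding volume as the primary outcome of the definitive trial. Appendix 5, item 10 of the principal investigators' roles, calls it the variable of greatest interest and describes three measurements: suction devices, weighed compresses and a calibrated vaginal collection bag. At the end of surgery "an objective estimate of bleeding will be made by adding the volume of bleeding from the suction devices", the compresses and the bag.

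Section 15 holds the three parts and the total as separate numeric variables. For the bleeding methods, section 9.14 plans one statistic, the coefficient of variation of each method within each technique, and the table shells in section 16 provide cells for it. Section 10.3 and the monitor functions in Appendix 5 require a check for missing data and a comparison of all primary and secondary outcome data with the clinical record.

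**The concern.** A feasibility study should return an answer to each part of its own question. Recruitment, randomisation and delivery of the assigned surgery all have an endpoint. Outcome measurement does not.

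The blood-loss procedure is demanding. The suction device must be marked at set moments to separate out amniotic fluid, irrigation volume must be subtracted, compresses must be weighed against known dry weights, and a specific bag must be supplied to three countries and placed before surgery. Whether three surgical teams can do all of this in most operations is a real feasibility question, and the planners of the definitive trial will need the answer. As planned, the study could be reported as feasible without stating in how many women its intended future primary outcome was obtained as specified.

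**Working it through.** **1. Research question against endpoints.**

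| Part of the question (section 4) | Endpoint in 8.1 |
|---|---|
| Recruit | Consent proportion; screening failure |
| Randomise | Split between arms |
| Intervene | Crossover |
| Measure outcomes | None directly; day-42 completion is the nearest |

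Of the five endpoints, none measures completeness of outcome measurement, and one is indirectly related.

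**2. Could another planned summary fill the gap?**
- *Day-42 completion.* The final contact is a telephone call (section 10.2.4). Reaching it does not show that suction, compresses and bag were all measured six weeks before.
- *Coefficient of variation.* This is SD / mean across women, within one method and one arm. It is computed on whatever values exist, so it does not show how many are absent. The three methods capture different compartments that are then added, so it does not show agreement either.
- *Table shells.* The clinical outcome table is headed with a total of 60, and the bleeding-method table has only coefficient-of-variation cells. Neither shows a number measured per row.
- *Monitoring.* Findings go to the coordinator and the investigators. They are not a planned study result.

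**3. What the missing endpoint would deliver.** The plan gives no figure on this point to reproduce. Its only sample-size arithmetic is 36 + 12 + 12 = 60, which is correct. If the 60 includes screening failures and the quoted upper figure of 22.6% applies, confirmed cases number 60 × (1 − 0.226) = 46.4, about 46. The completeness counts below are assumptions.

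| Women with all three parts | Percent | Exact 95% CI |
|---|---|---|
| 48/60 | 80% | 67.7% to 89.2% |
| 54/60 | 90% | 79.5% to 96.2% |
| 57/60 | 95% | 86.1% to 99.0% |
| 41/46 | 89% | 76.4% to 96.4% |
| 27/30 (one arm) | 90% | 73.5% to 97.9% |

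For 41/46 the Wilson interval is 77.0% to 95.3%. On that illustration, a definitive trial would recruit 46/41 = 1.12 times its evaluable number, or 1/0.770 = 1.30 times at the lower limit.

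**4. Why three parts matter.** If each part is measured with probability c, independently (an assumption), all three exist with probability c³:
- c = 0.90: 0.729, so 60 × 0.271 = 16.3 incomplete totals
- c = 0.95: 0.857, so 8.6 incomplete
- c = 0.98: 0.941, so 3.5 incomplete

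**5. Why handling of an unmeasured part matters.** If a part holding share s of the loss were summed as zero, that woman's total would fall by s. If this happened in a fraction m of women, unrelated to volume, the mean would fall by s × m. With an assumed bag share of 5% to 20% and m of 5% to 20%, one total falls by 5% to 20%, and the mean by 0.05 × 0.05 = 0.25% up to 0.20 × 0.20 = 4%.

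**The case against.** The strongest reply is that the data are largely there. Each part has its own variable, so completeness can be counted afterwards. Monitors compare all outcome data with the clinical record, and bleeding volume is a secondary endpoint. Section 10.2 defines follow-up as four moments, the first intraoperative and including total bleeding, so day-42 completion could be read as covering measurement. Appendix 5 assigns a team member to the bleeding measurements. The study is descriptive, and its case report form is still to be designed.

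Most of this stands, and it rules out several stronger readings that a reader might infer:
- *That the measurement question has no data behind it.* The separate components contradict this, provided an unmeasured part is kept distinct from zero.
- *That partial sums are stored as ordinary totals.* The documents say nothing on handling; they do not say this.
- *That zeros printed in the surgical note, such as "Estimated bleeding by calibrated vaginal collection bag: 00cc", are recorded values.* They look like format masks. Appendix 11 prints surgery times in the same style and repeats all three bleeding items with blank fields.
- *That omissions fall on the worst cases.* Nothing documents this. Entry requires scheduled surgery without active bleeding, the bag is placed beforehand, and compresses are weighed at the end.
- *That blood loss is singled out because histology has a code for unavailable results.* Other numeric variables in section 15 also lack such a code.

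What the reply does not supply is a reported result. Even on the broad reading of follow-up, a woman is counted as having completed it without any criterion for the three parts. Being derivable is not the same as being planned and reported.

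**Conclusion.** The point holds as a gap in the pre-specified endpoints and summaries. Section 4 and objective 6.1 ask whether outcomes can be measured, and nothing planned reports it, including for the variable intended as the definitive trial's primary outcome. The plan also does not say how a total with an unmeasured part is handled.

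The mapping of question to endpoints rests on the documents alone. The sizes do not: the 41/46 count, the per-part completeness rates, their independence and the 5% to 20% bag share are illustrative assumptions, and the denominator of 46 assumes that the 60 includes screening failures. No actual loss of data or bias is shown. This is a cheap improvement that lets the study answer its own question; it is not a flaw that invalidates the design.

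**What to change.** 1. Add to section 8.1: *Percentage of PAS-confirmed randomised women with all three bleeding components measured as in Appendix 5 item 10, by arm and centre*, with an exact or Wilson 95% confidence interval. Read the centre figures mainly as counts: with 12 women, even 12/12 has an exact lower limit of 0.025^(1/12) = 73.5%.
2. Show the number measured in each row of the bleeding tables in section 16.
3. In section 15, the case report form and Appendix 11, record each component as measured or not measured, distinct from 0 mL.
4. Flag any total with an unmeasured component, keep the components that were measured, and describe totals with and without the flagged cases. Deletion alone is not a safe rule. Suppose 41 women lose 2,000 mL and 5 lose 4,000 mL, and the omissions fall on those 5 (assumed only to show the risk). The true mean is 102,000/46 = 2,217 mL. Partial sums 20% too low give 98,000/46 = 2,130 mL (−3.9%); deleting the 5 totals gives 2,000 mL (−9.8%).

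The cost is one extra tabulated percentage and small wording changes to the protocol and case report form. Sample size and surgical care do not change.

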Women with a previous cesarean section, anterior placenta previa, and imaging (ultrasound or MRI) with signs suggestive of PAS will be eligible to participate (See Appendix 2: Definition of a suspected PAS case). Informed consent will be requested from these patients prior to surgery. Considering that these are pregnant women, the participation of the husband or spouse will be included in the informed consent (Appendix 7). In the event that the patient does not have a husband or spouse, the "Declaration of mother head of the family" will be filled out (Appendix 8).

Randomization will be carried out before starting the surgical procedure, with the aim of reducing the possibility of selection bias by the surgical team since there is no blinding.

It is possible that some patients who are eligible before surgery and who have signed the informed consent, will cease to be eligible if macroscopic signs suggestive of PAS are not found at laparotomy (See Appendix 2: Definition of confirmed PAS case) (that is, if present a false positive result of the prenatal diagnostic images), which has been described in up to 22.6%¹¹ of the cases. These patients will be considered screening failures in the recruitment process and will be excluded from the statistical analysis.

9.5.1. Inclusion criteria:

- Pregnant women over 18 years of age.
- History of previous cesarean section and anterior placenta previa
- Patients with prenatal diagnosis by ultrasound or MRI of PAS (See Appendix
 2: Definition of a suspected case of PAS), regardless of the suspected degree of severity of the disease.
- Requirement for surgical management of placental accreta on a scheduled basis.
- Patients without active vaginal bleeding in the period immediately before surgery (Patients entering the operating room without active bleeding).

9.5.2. Exclusion Criteria:

- Women without previous living children.

9.6. Sample size:

As the aim of the study is not to compare the effectiveness between interventions, a formal power calculation was not performed. A sample size of 60 participants. According to the estimated recruitment rate for each center, the following distribution is proposed: 36 patients from Indonesia, 12 patients from Argentina and 12 patients from Colombia to address the feasibility objectives.

9.7. Recruitment strategy:

9.7.1. Participant selection:

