Women with a previous cesarean section, anterior placenta previa, signs of PAS on ultrasound or prenatal magnetic resonance imaging (See Appendix 2: Suspicious case of

PAS) and who meet the inclusion criteria will be considered as possible candidates to participate in the study. Patients will be identified by the medical group and evaluated for their eligibility at the time of hospital admission before surgery.

Once the treating medical personnel confirm the eligibility of the patient, she will be provided with complete information about the study and the physical informed consent, the patient will have at least 48 hours to evaluate it, discuss it and decide whether or not she wishes to participate.

Participants who voluntarily decide to take part in the study will not receive any payment or remuneration as a result of their participation.

Some anonymized data of the women who decline their participation in the study and that will be used in the CONSORT report will include:

Date of cesarean section. Ethnicity Number of living children Reason why the patient is not eligible, or if she is eligible because she declined to participate.

Before the start of the surgical procedure, the clinical coordinator of the study will be in charge of revealing the surgical intervention to which the patient has been randomized to reduce the probability of selection bias since blinding is not possible in this study.

Once the laparotomy has been performed, the surgeon will define whether or not there are macroscopic signs on the anterior face of the uterus that confirm the diagnosis of PAS (See Appendix 2, Confirmed case of PAS). The clinical diagnostic criteria reported by the International Federation of Gynecology and Obstetrics (FIGO) will be used¹⁷.

At that time, if the diagnosis of PAS is confirmed, the randomized intervention will continue. If the diagnosis of PAS is not confirmed, the patient will be considered a screening failure.

The entire process from the disclosure of the randomization, the confirmation or exclusion of PAS and the performance of the randomized intervention will be supervised by the study coordinator in each hospital.

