Informed consent will be obtained before the participant undergoing any trial-related intervention. Because this study considers a vulnerable population (pregnant women) as the reference population, the informed consent is based on resolution 8430, article 30, where it is contemplated that the informed consent of the woman and her spouse must be obtained, prior information from the possible risks for the embryo, fetus or newborn in your case. If informed consent cannot be obtained from the spouse, there will be a statement from the mother head of the family where the study participant certifies that she is economically and socially responsible for her minor children (Appendix 8).

The principal investigator retains overall responsibility for conducting research on his site, this includes obtaining informed consent from participants on his site. They must ensure that any person to whom the responsibility of participating in the informed consent process is delegated is duly authorized, trained, and competent to participate in accordance with the ethically approved protocol, the principles of Good Clinical Practice (GCP), and the Declaration of Helsinki. If a delegation of consent is acceptable, details must be provided.

The participant will remain free to withdraw at any time from the trial without giving reasons and without jeopardizing her further treatment and will be provided with a point of contact where she can obtain further information about the trial. The data collected up to the time of withdrawal will only be used after withdrawal if the participant has consented to it. Any intention to use such data will be described in the consent literature. When a participant is required to give her consent again or a participant is required to provide new information, it will be the responsibility of the principal investigator to ensure that this is done promptly.

The Principal Investigator at each site assumes responsibility for ensuring that all vulnerable participants are protected and voluntarily participate in an environment free from coercion or undue influence.

Consent will include the use of anonymous images (ultrasound or MRI), photographic and video recording of operative findings, as well as histopathology slides for independent review by blind experts.

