Use of vascular interventions	What type of vascular intervention was used during the surgical management of PAS	Qualitative nominal	 1.None Ligation of internal iliac arteries Endovascular occlusion of the internal or common iliac arteries (balloons) Clamping or ligation of the aorta Aortic endovascular occlusion (Balloon) Manual compression of the aorta 	Frequency and percentages
Use of cell saver	Cell saver was used during the surgical management of PAS	Qualitative nominal	0.NO 1. YES	Frequency and percentages
start surgery hour	Start surgery hour	NA	Hours and minutes	
End surgery hour	End surgery hour	NA	Hours and minutes	
Duration of surgery	Duration of the surgical procedure in min	Qualitative nominal	Number	Tendency and dispersion
Hystological confirmation of PAS	Hystopathology reports a excluyent or confirmative diagnosis of PAS	Qualitative nominal	0. NO 1. YES 2. NON AVAILABLE HYSTOPATHOLOGY	Frequency and percentages

PAS invasión degree	Most high degree	Qualitative	0.	Accreta	Frequency and
related with	of PAS according	nominal	1.	Inccreta	percentages
hystopathology	hystopathology		2.	Percreta	

Clinical outcomes						
Variable	Definition	Tipe of	Operative leve	Outcome		
		variable	-	measure		
Intra-surgical	Total blood loss	Continuous	Number	Tendency and		
bleeding volumen for	during the	quantitative		dispersion		
pads stimation	procedure for pads	1		1		
•	calculation					
Intra-surgical	Total blood loss	Continuous	Number	Tendency and		
bleeding volumen for	during the	quantitative		dispersion		
suction stimation	procedure for	1		1		
	suction calculation					
Intra-surgical	Total blood loss	Continuous	Number	Tendency and		
bleeding volumen for	during the	quantitative		dispersión		
Reolecting bag	procedure for	1		Ĩ		
stimation	recollecting bag					
	calculation					
Intra-surgical	Total blood loss	Continuous	Number	Tendency and		
bleeding volumen	during the	quantitative		dispersion		
	procedure	•		-		
Hospital admission	Hospital admission	NA	Day/month/year	NA		
date	patient date					
Hospital discharge	Hospital discharge	NA	Day/month/year	NA		
date	patient date					
Numbers of day in-	Total numbers of	Continuous	Number	Tendency and		
hospital	day in-hospital	quantitative		dispersion		
Numbers of day of	Total numbers of	Continuous	Number	Tendency and		
postoperative stay at	day of	quantitative		dispersion		
hospital	postoperative stay					
	at hospital					
Admission to intensive	The patient was	Qualitative	0. NO	Frequency and		

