Appendix 10: standardized surgical techniques and intra-operative imaging manual

Technical conditions for intraoperative imaging:

1. The taking of photos and videos will be performed by the sub-investigator or delegated to a member of the surgical team in case the sub-investigator is not available.

2. The photo taker will use all necessary biosafety items to enter the surgical field.

3. The taking of photos and videos may be done by means of a mobile device camera or a standard or professional camera.

4. The taking of photos and videos will be done in a medium, short or detailed photographic plane according to the photographic moment to be captured.

5. The photos of the resected macroscopic piece (uterus, uterine segment or placenta) will be taken on a clean background to improve its visualization.

6. The format of captured images should be JPEG and the video format should be MP4.

7. The maximum duration of each video will be 30 seconds.

Description of the surgical technique:

Asepsis and antisepsis of skin and vagina 2.

Skin incision: Vertical or horizontal.

- 3. Fascia incision: Vertical or horizontal
- 4. Dissection by planes up to the abdominal cavity
- 5. Identification of findings: (Take photo presence or absence of PAD).
- 6. Intraoperative staging:
 - a. Opening of the right parametrium: (Take photo)
 - b. Left parametrial opening: (Take photo)
 - c. Retrovesical dissection: (Take photo)
 - d. Vesicouterine bypass: description of the findings (fibrosis?)
- 7. Hysterotomy:
- 8. Management of placenta previa or placenta previa: Ward's maneuver.

9. Fetal extraction: time, presentation, weight, length, APGAR, amniotic fluid characteristics.

- a. Clamping, cutting and ligation of the umbilical cord.
- b. Delivery: Does spontaneous delivery occur? Yes/No
- 10. Hysterotomy management: Hysterorrhaphy or hemostasis with forceps?
- 11. Vesicouterine dissection is completed
- 12. Partial myometrial resection vs. total or subtotal hysterectomy.

a. Partial myometrial resection:

i. Hemostatic sutures obliterating colpouterine pedicles.

ii. Resection of abnormal myometrium (segmentectomy) with attached placenta (Take photo).

- iii. Complete placental delivery
- iv. Control of bleeding placental insertion bed (if applicable).

v. Uterine reconstruction with two layers of suture, the first with "U" stitches and the second with invaginating uninterrupted suture (Take photo).

vi. Revision of hemostasis of the anterior face of the uterus and

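### Women judged free of PAS at laparotomy leave the analysis, so Objective 3 cannot describe absence of PAS, and the surgeon's negative verdict has no tabulated check and no breakdown by arm

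*Combined protocol and SAP*

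**What the plan says.** Objective 3 (section 6.2) reads: "To describe the confirmation of the presence or absence of placental accretenotic spectrum in each case". It covers presence and absence of PAS, and covers every case. Section 8.1 lists "Screening failure percentage" as a primary endpoint, and section 15 defines it as women who consented but in whom PAS was ruled out during surgery.

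The verdict belongs to the operating team. Under 9.7.1, once the abdomen is open, "the surgeon will define whether or not there are macroscopic signs on the anterior face of the uterus that confirm the diagnosis of PAS". The allocation is known by then: according to 9.4, "Randomization will be carried out before starting the surgical procedure", and 9.7.1, 9.12 and Appendix 5 have the coordinator reveal it before surgery starts. Under 9.11 a woman ruled out leaves the study and her further surgery is left to the treating team. Under 9.4 she also leaves the statistical analysis.

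Three sources could be set against the surgeon's verdict:

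- **Histology.** Section 15 has a variable, "Hystopathology reports a excluyent or confirmative diagnosis of PAS", coded no, yes or not available, and Table 3 has a row for it.
- **Images.** Section 9.7.1 has all surgery photographed and filmed as quality control, including findings that rule PAS out. Appendix 10, step 5, adds "Take photo presence or absence of PAD".
- **Blind review.** Section 11.2 says that consent will cover images and "histopathology slides for independent review by blind experts". Section 15 has no variable for the result, and section 16 no row.

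**The concern.** An objective about presence or absence in each case needs an analysis set that contains both. The set behind Table 3 contains only women already called PAS, and its FIGO row starts at grade 1. In that table, confirmation at laparotomy is 100% by construction. Absence can enter only as a negative histology result in a retained woman. A woman wrongly called free of PAS cannot appear at all.

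That direction matters because the negative verdict forms a primary endpoint, decides who stays in the study, and is given by a surgeon who knows the arm. If rule-outs were more frequent in one arm, the retained groups would no longer be the groups that were randomised. The definitive trial needs to know whether this happens before it settles how PAS is to be confirmed.

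The point concerns what Objective 3 can show. Which set the clinical tables should use is a separate question.

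**Working it through.** No figure in the plan needs reproducing: 9.6 states that no power calculation was done. The centre split adds up (36 + 12 + 12 = 60).

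**1. What can appear in the tables**

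| Surgeon's verdict | Truth: PAS | Truth: no PAS |
|---|---|---|
| PAS (retained) | Table 3, histology yes | Table 3, histology no |
| No PAS (ruled out) | in no table of section 16 | in no table of section 16 |

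The lower row reaches the report only as an undivided count, the screening-failure percentage.

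**2. How many women are in the lower row**

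Input: the false-positive rate in 9.4, given as up to 22.6% and used here as a planning value.

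- If 60 means randomised: 60 × 0.226 = 13.6, about 14 ruled out and 46 retained.
- If 60 means confirmed, as the study groups in 9.3 and the n=60 table headers suggest: 60 / (1 − 0.226) = 77.5, so 78 randomised, of whom 78 × 0.226 = 17.6, about 18, are ruled out.

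**3. Why histology in retained women does not reveal missed cases**

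Let q be the true proportion without PAS, and Se and Sp the surgeon's sensitivity and specificity for PAS. Then

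- observed rule-out proportion = q·Sp + (1 − q)(1 − Se)
- PAS among those ruled out = (1 − q)(1 − Se) / observed rule-out proportion
- PAS among those retained = (1 − q)·Se / (1 − observed rule-out proportion)

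Se and Sp are assumptions, q = 0.226 is taken as the true proportion, and histology is treated as error-free.

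| Se | Sp | Observed rule-out | PAS among retained | PAS among ruled out |
|---|---|---|---|---|
| 1.00 | 1.00 | 22.6% | 100% | 0% |
| 1.00 | 0.80 | 18.1% | 94.5% | 0% |
| 0.90 | 1.00 | 30.3% | 100% | 25.5% |
| 0.85 | 1.00 | 34.2% | 100% | 33.9% |

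For the third row: 0.226 + 0.774 × 0.10 = 0.303, and 0.0774 / 0.303 = 25.5%. Rows 1, 3 and 4 give the same histology result in Table 3, although the share of missed cases runs from none to a third.

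**4. What a check could deliver**

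If n ruled-out women are checked and no missed case is found, the upper end of the exact two-sided 95% interval is 1 − 0.025^(1/n).

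- n = 14: 23.2%
- n = 18: 18.5%
- n = 7 (about half of 14, one arm): 41%

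**5. Whether a missed case is plausible under the protocol's own definitions**

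Appendix 5 (item 8a) places the verdict before the uterus is opened. Appendix 2 describes accreta as a uterus without obvious bulge or surface invasion and with little or no new vascularity. Its other accreta criteria, failure to separate and heavy bleeding on attempted removal, arise after delivery. Section 2 puts accreta at 64.6% of cases. Section 9.11 describes a further confirmation by failed separation in the hysterectomy arm but not in the resection arm. These passages need reconciling. They leave room both for missed cases and for a difference between arms.

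**The case against.** A reader might infer that the surgeon's verdict is never checked. The documents do not support that. Histology has a negative code and a Table 3 row, so a wrong positive verdict can show. All operations are filmed and photographed for quality control, rule-outs included, and the coordinator supervises the confirmation or exclusion of PAS. Screening failure is itself a recorded and reported variable. What is left is narrower: the negative verdict has no check in the analysis.

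Endpoint 2 can also be defended as operational. Section 15 defines it as ruled out during surgery, so the rate at which women leave the pathway is counted correctly even if some verdicts are wrong. That stands for endpoint 2, but Objective 3 asks for more than a count.

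A reader might further infer that blinded review of the step-5 photographs would settle the matter. It would not. They are taken before hysterotomy and cannot show the accreta criteria that arise after delivery. Histology has a limit as well: there may be no specimen where nothing was resected.

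The numbers are small, too. With about 7 ruled-out women per arm, no comparison of error rates between arms is possible. This stands, and it limits the remedy to description.

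Finally, the blind review is known only from 11.2. The consent form was not available for this review and may say more.

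**Conclusion.** The concern holds in a limited form. Followed as written, the plan describes absence of PAS only as a screening-failure count. It tests positive verdicts against histology and cannot show a wrong negative verdict or an imbalance of rule-outs between arms. The group concerned is about 14 of 60 randomised women, or about 18 of 78, if the protocol's upper figure of 22.6% applies. Even a complete check with no missed case would leave an upper limit of about 23% or 18.5%, and a wider one if histology is missing for some women.

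The misclassification figures illustrate the mechanism under assumed accuracy. They are not evidence that the surgeons err. Nor do the documents show that rule-outs will differ by arm, only that the plan would not display it if they did. The change is worth making because its main part uses data that the plan already collects or can obtain at little cost.

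**What to change.** In 9.14 and section 16:

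1. State that Objective 3 is analysed in every randomised woman who had the laparotomy, including those ruled out.
2. Report the number and percentage ruled out by assigned arm.
3. Add one table of surgeon's verdict (PAS, no PAS) by histology (yes, no, not available), by arm.
4. Add a level for no PAS to the FIGO variable and its Table 3 row.
5. If the blind review named in 11.2 is carried out, add a variable for its result (yes, no, not assessable), name who reads and how disagreement is resolved, and include it in the same table. Base it on all surgical images and video, not on the step-5 photographs alone.
6. Present everything descriptively with exact intervals and no test between arms.

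Cost: one extra table, and verdict and histology data kept for women who have left the study, so the consent and ethics approval should be checked to confirm that they cover this. The blind review is secondary. It adds reader time for about 60 to 78 image sets and yields limited precision. No treatment rule changes.
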